16.1 Appendix 1: Pembrolizumab Dose Modification Guidelines

Table 16-1 Dose Modification and Toxicity management Guidelines for Immune-related Adverse Events associated with Pembrolizumab

General instructions:				
Immune related AEs	Toxicity grade or conditions (CTCAEv4.0)	Action taken to pembrolizumab	irAE management with corticosteroid and/or other therapies	Monitor and follow-up
Pneumonitis	Grade 2	Withhold	
Administer corticosteroids (initial dose of 1-2 mg/kg prednisone or equivalent) followed by taper	
Monitor participants for signs and symptoms of pneumonitisEvaluate participants with suspected pneumonitis with radiographic imaging and initiate corticosteroid treatmentAdd prophylactic antibiotics for opportunistic infections
	Grade 3 or 4, or recurrent Grade 2	Permanently discontinue		
Diarrhea / Colitis	Grade 2 or 3	Withhold	
Administer corticosteroids (initial dose of 1-2 mg/kg	
Monitor participants for signs and symptoms of enterocolitis (ie,
	Grade 4	Permanently discontinue		

General instructions:				
Immune related AEs	Toxicity grade or conditions (CTCAEv4.0)	Action taken to pembrolizumab	irAE management with corticosteroid and/or other therapies	Monitor and follow-up
			
prednisone or equivalent) followed by taper
 
Participants with \geq Grade 2 diarrhea suspecting colitis should consider GI consultation and performing endoscopy to rule out colitisParticipants with diarrhea/colitis should be advised to drink liberal quantities of clear fluids. If sufficient oral fluid intake is not feasible, fluid and electrolytes should be substituted via IV infusion	
diarrhea, abdominal pain, blood or mucus in stool with or without fever) and of bowel perforation (ie, peritoneal signs and ileus)
 
Participants with \geq Grade 2 diarrhea suspecting colitis should consider GI consultation and performing endoscopy to rule out colitisParticipants with diarrhea/colitis should be advised to drink liberal quantities of clear fluids. If sufficient oral fluid intake is not feasible, fluid and electrolytes should be substituted via IV infusion

General instructions: 
 1. Corticosteroids taper should be initiated upon AE improving to Grade 1 or less and continue to taper over at least 4 weeks. 2. For situations where pembrolizumab has been withheld, pembrolizumab can be resumed after AE has been reduced to Grade 1 or 0 and corticosteroid has been tapered. 3. For severe and life-threatening irAEs, IV corticosteroid should be initiated first followed by oral steroid. Other immunosuppressive treatment should be initiated if irAEs cannot be controlled by corticosteroids. 				
Immune related AEs	Toxicity grade or conditions (CTCAEv4.0)	Action taken to pembrolizumab	irAE management with corticosteroid and/or other therapies	Monitor and follow-up
AST /ALT elevation or Increased bilirubin	Grade 2	Withhold	
 • Administer corticosteroids (initial dose of 0.5-1 mg/kg prednisone or equivalent) followed by taper 	
 • Monitor with liver function tests (consider weekly or more frequently until liver enzyme value returned to baseline or is stable).
	Grade 3 or 4	Permanently discontinue	
 • Administer corticosteroids (initial dose of 1-2 mg/kg prednisone or equivalent) followed by taper 	
Type 1 diabetes mellitus (T1DM) or Hyperglycemia	Newly onset T1DM or Grade 3 or 4 hyperglycemia associated with evidence of beta-cell failure	Withhold	
 • Initiate insulin replacement therapy for participants with T1DM • Administer anti-hyperglycemic in participants with hyperglycemia 	
 • Monitor participants for hyperglycemia or other signs and symptoms of diabetes.
Hypophysitis	Grade 2	Withhold	
 • Administer corticosteroids and initiate hormonal replacements as clinically indicated. 	
 • Monitor for signs and symptoms of hypophysitis (including
	Grade 3 or 4	Withhold or permanently discontinue ¹		

General instructions: 
 1. Corticosteroids taper should be initiated upon AE improving to Grade 1 or less and continue to taper over at least 4 weeks. 2. For situations where pembrolizumab has been withheld, pembrolizumab can be resumed after AE has been reduced to Grade 1 or 0 and corticosteroid has been tapered. 3. For severe and life-threatening irAEs, IV corticosteroid should be initiated first followed by oral steroid. Other immunosuppressive treatment should be initiated if irAEs cannot be controlled by corticosteroids. 				
Immune related AEs	Toxicity grade or conditions (CTCAEv4.0)	Action taken to pembrolizumab	irAE management with corticosteroid and/or other therapies	Monitor and follow-up
				hypopituitarism and adrenal insufficiency)
Hyperthyroidism	Grade 2	Continue	
 • Treat with non-selective beta-blockers (eg, propranolol) or thionamides as appropriate 	
 • Monitor for signs and symptoms of thyroid disorders.
	Grade 3 or 4	Withhold or permanently discontinue ¹		
Hypothyroidism	Grade 2-4	Continue	
 • Initiate thyroid replacement hormones (eg, levothyroxine or liothyroinine) per standard of care 	
 • Monitor for signs and symptoms of thyroid disorders.
Nephritis and Renal dysfunction	Grade 2	Withhold	
 • Administer corticosteroids (initial dose of 1-2 mg/kg prednisone or equivalent) followed by taper 	
 • Monitor changes of renal function
	Grade 3 or 4	Permanently discontinue		
Myocarditis	Grade 1 or 2	Withhold	
 • Based on severity of AE, administer corticosteroids 	
 • Ensure adequate evaluation to confirm etiology and/or exclude other causes
	Grade 3 or 4	Permanently discontinue		
All other immune-related AEs	Intolerable/persistent Grade 2	Withhold		

General instructions:

1. Corticosteroids taper should be initiated upon AE improving to Grade 1 or less and continue to taper over at least 4 weeks.
2. For situations where pembrolizumab has been withheld, pembrolizumab can be resumed after AE has been reduced to Grade 1 or 0 and corticosteroid has been tapered.
3. For severe and life-threatening irAEs, IV corticosteroid should be initiated first followed by oral steroid. Other immunosuppressive treatment should be initiated if irAEs cannot be controlled by corticosteroids.

Immune related AEs	Toxicity grade or conditions (CTCAEv4.0)	Action taken to pembrolizumab	irAE management with corticosteroid and/or other therapies	Monitor and follow-up
	Grade 3	Withhold or discontinue based on the type of event. Events that require discontinuation include and not limited to: Gullain-Barre Syndrome, encephalitis	
• Based on type and severity of AE, administer corticosteroids	
• Ensure adequate evaluation to confirm etiology and/or exclude other causes
	Grade 4 or recurrent Grade 3	Permanently discontinue		

16.2 Appendix 2: Medications to be used with caution with canakinumab while on study

Table 16-2 CYP3A substrates with narrow therapeutic index, or sensitive CYP2C9 substrates with therapeutic index**

CYP2C9 substrates with narrow therapeutic index			
warfarin	phenytoin		
CYP3A4/5 substrates with narrow therapeutic index			
astemizole*	diergotamine	pimozide	alfentanil
cisapride*	ergotamine	quinidine*	terfenadine*
cyclosporine	fentanyl	tacrolimus	sirolimus

*Compounds known to increase QTc interval that are also primarily metabolized by CYP3A4/5.
For an updated list of CYP2C9 substrates, CYP3A substrates, inhibitors and inducers, please reference the Novartis Oncology Clinical Pharmacology internal memo: drug-drug interactions (DDI) database, October 2010, which is compiled primarily from the FDA's "Guidance for Industry, Drug Interaction Studies", the Indiana University School of Medicine's Drug Interactions Database, and the University of Washington's Drug Interaction Database.
**Sensitive substrates: Drugs that exhibit an AUC ratio (AUCi/AUC) of 5-fold or more when co-administered with a known potent inhibitor. Substrates with narrow therapeutic index (NTI): Drugs whose exposure-response indicates that increases in their exposure levels by the concomitant use of potent inhibitors may lead to serious safety concerns (e.g., Torsades de Pointes).

16.3 Appendix 3: Guidelines for Response, Duration of Overall Response, TTF, TTP, Progression-Free Survival, and Overall Survival (based on RECIST 1.1)

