6.7.2 Instruction for prescribing and taking study treatment

Administration of study treatment

Canakinumab (one syringe of 1 mL and one syringe of 0.5mL) will be administered by study site personnel via s.c. injections once every 3 weeks.

Pembrolizumab will be administered by study site personnel via i.v. infusion once every 3 weeks as per locally approved label and local practice.

For combination arm, study drugs should be administered sequentially, on the same day (canakinumab 200mg s.c injection then 30 minutes later pembrolizumab 200 mg i.v. infusion during 30 minutes)

The infusion time reported for pembrolizumab (30 min: -5 min/+10 min) is suggestion only. The locally approved label and local practice is to be followed.

Table 6-4 Dose and treatment schedule

Investigational / Control Drug (Name and Strength)	Dose	Frequency and/or Regimen
Canakinumab 200mg	200mg (1 X 150mg/1mL syring and 1x 50mg/0.5mL syringe)	C1D1 (Day 1) and C2D1 (Day 22)
Pembrolizumab 200mg	200mg (refer to Table 6-1)	C1D1 (Day 1) and C2D1 (Day 22)

7 Informed consent procedures

Eligible subjects may only be included in the study after providing (witnessed, where required by law or regulation) Institutional Review Board/Independent Ethics Committee (IRB/IEC) approved informed consent.

If applicable, in cases where the subject's representative(s) gives consent (if allowed according to local requirements), the subject must be informed about the study to the extent possible given

his/her understanding. If the subject is capable of doing so, he/she must indicate agreement by personally signing and dating the written informed consent document.

Informed consent must be obtained before conducting any study-specific procedures (e.g. all of the procedures described in the protocol). The process of obtaining informed consent must be documented in the subject source documents.

Novartis will provide to investigators in a separate document a proposed ICF that complies with the International Council for Harmonisation of Technical Requirements for Pharmaceuticals for Human Use' (ICH) Good Clinical Practice (GCP) guidelines and regulatory requirements and is considered appropriate for this study. Any changes to the proposed consent form suggested by the investigator must be agreed by Novartis before submission to the IRB/IEC.

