Information about common side effects already known about the investigational drug can be found in the IB and/or Core Data Sheet (CDS) for marketed drugs. This information will be included in the subject informed consent and should be discussed with the subject during the study as needed. Any new information regarding the safety profile of the investigational drug that is identified between IB updates will be communicated as appropriate, for example, via an investigator notification (IN) or an aggregate safety finding. New information might require an update to the informed consent and then must be discussed with the subject.

The following informed consents are included in this study:

- Main study consent, which also included:
 - A subsection that requires a separate signature for the 'Optional Consent for Additional Research' to allow future research on data/samples collected during this study
 - Pregnancy Outcomes Reporting Consent for female subjects

Women of child bearing potential must be informed that taking the study treatment may involve unknown risks to the fetus if pregnancy were to occur during the study and agree that in order to participate in the study they must adhere to the contraception requirements.

A copy of the approved version of all consent forms must be provided to Novartis after IRB/IEC approval.

Subjects might be asked to complete an optional questionnaire to provide feedback on their clinical trial experience (please refer to [Section 8.5.4.1](#)).

8 Visit schedule and assessments

The assessment schedule [Table 8-2](#) lists all of the assessments and indicates with an "X", the visits when they are performed. Note: when the assessment is indicated with an "S", this will be documented in the subject source medical record only. All data obtained from these assessments (indicated with an "X" and "S") must be supported in the subject's source documentation.

Treatment cycles are intended to be 3 weeks (21 days), but the treatment can be delayed in order to manage toxicities according to the canakinumab dose modification criteria in [Section 6.5.1](#) and the locally approved label and local practice for pembrolizumab. During

the course of the study visits, test procedures should occur on schedule whenever possible as per allowable visit windows specified in [Table 8-1](#) below.

Table 8-1 Allowable visit windows are specified as follow:

Visit name	Window
Screening	-1 to -28 Days before Cycle 1 Day 1

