All assessments including C1D1, during the treatment period (except tumor assessments)	± 3 Days (-3 days for Cycle 1 Day 1)
Canakinumab injection (if applicable)	± 3 Days
Pembrolizumab infusion (if applicable)	± 3 Days
PK/IG/PD sampling	Refer to tables in Section 8.5.1
26, 52, 78 and 104 day safety follow-up visits	± 7 Days
130-day safety follow-up visit	+ 14 Days
EOT	≤ 21 Days after permanent discontinuation of study treatment, but before the surgery
EOT biomarker sampling	At time of surgery if possible, if not within 4 days prior to surgery

Subjects should be seen for all visits/assessments as outlined in the assessment schedule ([Table 8-2](#)) or as close to the designated day/time as possible. Missed or rescheduled visits should not lead to automatic discontinuation. Subjects who prematurely discontinue the study for any reason should be scheduled for a visit as soon as possible, at which time all of the assessments listed for the final and safety follow-up visits will be performed. At this final visit, the AE and concomitant medications should be recorded on the case report form (CRF).

Table 8-2 Assessment Schedule

Period	Screening	Treatment		EOT		Safety Follow-up					EOS
Cycle		Cycle 1	Cycle 2								
Visit Name	Screening	Treatment C1D1	Treatment C2D1	EOT	Surgery	Safety Follow-up 1	Safety Follow-up 2	Safety Follow-up 3	Safety Follow-up 4	Safety Follow-up 5	EOS
Days	-28 to -1	1	22	When applicable ⁶	4 to 6 weeks	From EOT: 26	From EOT: 52	From EOT: 78	From EOT: 104	From EOT: 130	-
Non-drug therapies and procedures	From 28 days prior to day 1 until 130 days after EOT or start of new antineoplastic therapy, whichever is sooner. After start of a new antineoplastic therapy, only report non-drug therapies for AEs/SAEs suspected to be related to study treatment.										
Adverse Events	Continuous, up to 130 days after last dose of study treatment. After starting a new antineoplastic therapy, only report AEs suspected to be related to study treatment.										
Serious Adverse Events	Continuous, up to 130 days after last dose of study treatment. After starting a new antineoplastic therapy only report SAEs suspected to be related to study treatment.										
Serum Pregnancy Test	X			X							
Urine Pregnancy Test ²		S	S			S		S		S	
PET-CT (with diagnostic quality CT)	X			To be performed within 7 days prior to surgery							
CT/MRI - Thorax, Abdomen, Pelvis (if no diagnosis PET-CT captured)	X			To be performed within 7 days prior to surgery							

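### In Table 16-1 the Myocarditis row withholds pembrolizumab at Grade 1, yet the general rule lets it resume at Grade 1; a Grade 0 release condition for that row would remove the conflict

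*Protocol*

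**What the plan says.** Protocol Section 6.5.1 sends pembrolizumab dose modification to the locally approved label and local clinical practice. Where the drug is not yet approved, it refers to Section 16.1, Table 16-1.

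In that table:

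- General instruction 1 starts the steroid taper once the event is at Grade 1 or less and requires sites to "continue to taper over at least 4 weeks".
- General instruction 2 gives a single release rule for every withheld event: "pembrolizumab can be resumed after AE has been reduced to Grade 1 or 0 and corticosteroid has been tapered".
- The Myocarditis row withholds at Grade 1 or 2 and discontinues permanently at Grade 3 or 4. Its steroid entry is "Based on severity of AE, administer corticosteroids". It states no release condition of its own, and neither document mentions myocarditis anywhere else.

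Doses are planned for Day 1 and Day 22 (Table 6-4), with a window of 3 days either side (Table 8-1). Section 8 says "the treatment can be delayed in order to manage toxicities", but for pembrolizumab it ties this to the local label and local practice. Section 3 caps treatment at 6 weeks (2 cycles) and places surgery 4 to 6 weeks after the first dose; later surgery is tolerated but discouraged.

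Section 9.1.1 makes discontinuation mandatory on two separate grounds: when the investigator believes continuing would harm the subject, and in any situation where participation might create a safety risk.

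**The concern.** A hold rule and a release rule should not share a grade. Here they share Grade 1. A subject whose myocarditis improves from Grade 2 to Grade 1 meets the general release rule while still at a grade for which the row says to withhold.

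An event that begins at Grade 1 is also unclear. If it counts as already at the release grade, the Grade 1 hold cancels itself when no steroid is given. If it cannot be said to have been reduced to Grade 1, it must reach Grade 0, and the milder event then faces the stricter rule.

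At stake is a second pembrolizumab dose, shortly before thoracic surgery, in a subject whose myocarditis has not fully resolved. Scheduled testing adds little protection: the only planned ECG is before the first dose (Section 8.4.2), and Table 8-4 lists no troponin. The written grade therefore carries much of the weight.

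**Working it through.** The plan gives no figure on this point, so there is none to reproduce. The check compares the rules directly, then looks at timing and size.

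**1. Overlap in Table 16-1.** The release set from General instruction 2 is {0, 1}. For each category that can be withheld, intersect the hold grades with that set.

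| Category | Grades at which a hold is possible | Shared with {0, 1} |
|---|---|---|
| Pneumonitis | 2 | none |
| Diarrhea/colitis | 2, 3 | none |
| AST/ALT or bilirubin | 2 | none |
| Type 1 diabetes/hyperglycemia | 3, 4 (new-onset diabetes ungraded) | none by stated grade |
| Hypophysitis | 2, 3, 4 | none |
| Hyperthyroidism | 3, 4 | none |
| Nephritis/renal dysfunction | 2 | none |
| Myocarditis | 1, 2 | **1** |
| All other immune-related events | 2, 3 | none |

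Hypothyroidism is left out because treatment continues. Two rows need their wording checked. The residual category starts its hold at "Intolerable/persistent Grade 2". The diabetes row reads "Newly onset T1DM or Grade 3 or 4 hyperglycemia associated with evidence of beta-cell failure", so its only graded part starts at Grade 3. Result: 1 overlap in 9 categories.

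**2. Comparison with canakinumab.** Table 6-2 has 8 graded interruption rows, given here as hold grade, then highest release grade: general guidance 3, 2; neutropenia 2, 1; thrombocytopenia 3, 1; creatinine 3, 2; bilirubin 3, 1; AST/ALT above 5 to 10 times the upper limit of normal 3, 1; pancreatitis 3, 1; hypertension 3, 1. Every release grade lies below its hold grade, so 0 of 8 overlap.

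**3. Timing of the second dose.**

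- Dose window: 22 − 3 = Day 19 to 22 + 3 = Day 25.
- With steroids and a full taper of at least 28 days, the absolute bound is 1 + 28 = Day 29, which is 29 − 25 = 4 days past the window. That bound has the taper starting on the day of the first dose. A start on Day 2 gives 2 + 28 = Day 30.
- The 6-week cap ends at 1 + 42 = Day 43. To dose by then, the taper must start by 43 − 28 = Day 15. A steroid-treated subject could be re-dosed at Grade 1 only in a delayed slot of about Day 30 to 43, or if the release rule is read as met once the taper has begun.
- Without steroids there is no taper to wait for, and a Grade 1 subject may be dosed in the Day 19 to 25 window as the text stands.

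**4. Size.** Planned subjects given pembrolizumab: 44 (combination) + 22 (monotherapy) = 66. The share at sites governed by Table 16-1 is not stated, so the range is 0 to 66. No myocarditis incidence is given. At the ceiling, fewer than one case of any grade is expected unless incidence exceeds 1/66 ≈ 1.5%. This is a threshold, not an estimate.

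**5. After the fix.** Hold {1, 2} and release {0} share nothing, and no graded row of the table overlaps.

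**The case against.** The strongest reply is that the protocol already stops this dose. Section 9.1.1 requires discontinuation in any situation that might pose a safety risk. That trigger depends neither on the investigator's belief nor on a grade, and persisting myocarditis plainly fits it. A reader might infer from the overlap that nothing else in the protocol stands between such a subject and a second dose. The documents do not support that. What remains is that an ungraded catch-all does not settle which of two graded statements in the same table governs. The rule in Section 6.5.1.1 to follow the more conservative modification does not settle it either, because it covers conflicts between the two drugs.

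Second, the texts can be reconciled. Instruction 2 is a permission and the row is a prohibition, so obeying both means resuming only at Grade 0. That is a sensible reading and matches the proposed fix, but the table does not say that the row prevails.

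Third, a reader might infer that steroid-treated subjects could routinely be re-dosed at Grade 1. The taper and the 6-week cap largely exclude this, and a delay of pembrolizumab is tied to local label and practice. This objection stands and narrows the point mainly to subjects not given steroids. Even that path depends on reading the row's steroid wording as leaving steroids optional at low grade. The wording could instead mean that severity sets the dose.

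Fourth, Table 6-2 concerns another drug, and Grade 0 is not the only remedy: permanent discontinuation at any grade would also remove the overlap. Both remarks are fair. The Table 6-2 comparison shows only that the overlap is not a general convention of this protocol.

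Finally, the text of the table's footnote 1 is not visible in the copy reviewed. It is attached to Hypophysitis and Hyperthyroidism, not to Myocarditis, so it does not bear on the overlap.

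**Conclusion.** The point holds as a minor patient-safety wording issue, worth considering because the remedy is cheap. The hold and release grades overlap at Grade 1 in the Myocarditis row and in no other graded row. The consequence is confined to sites without local approval of pembrolizumab, and mainly to a Day 22 dose in a subject who received no steroids. Section 9.1.1 offers a general backstop.

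The expected effect in this trial is very small and possibly zero. This rests on the ceiling of 66 planned subjects, an unknown split of sites and an unstated incidence. SAP Section 1 records a recruitment halt on 1 February 2022, given the number already randomised and the difficulty of recruiting, which limits any effect further.

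A reader might also infer some effect on the primary result. There is none: discontinuation before surgery is handled by treatment policy (Protocol Section 12.4.2), and sample size, power and error rates are untouched.

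**What to change.** Add one line to the Myocarditis row of Table 16-1: *Resume only after resolution to Grade 0 and, if steroids were given, after corticosteroid taper; otherwise do not give the second dose. This overrides general instruction 2.*

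The cost is that a rare subject forgoes the second pembrolizumab dose. Confirming resolution may need an unscheduled ECG, which Section 8.4.2 already allows. The sample size, visit schedule and analysis do not change.

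The benefit in this trial is limited by the halt. Assume the last subject was randomised between 1 February 2022 and the end of a 28-day screening period begun that day. The 6-week treatment period then ended between 15 March 2022 (42 days later) and 12 April 2022 (28 + 42 = 70 days later), apart from toxicity delays. After that the line protects no one in this study and serves mainly as a correction for any later protocol that reuses the table.
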